8.4.2 Listings of Hematology, Clinical chemistry and Coagulation

- Separate listings will be provided for hematology, clinical chemistry and coagulation parameters.
- Data listings will be prepared for all laboratory parameters outside normal limits. In these listings the • values will be presented in the units in which they have been determined and in the standard units provided above, the sampling date, the clinical relevance (yes/no) as well as causa relationship if clinically relevant.

8.5 Urinalysis

Laboratory parameters are analyzed at Screening, Visit 3 (Day 56), Visit 6 (Day 224) and ET visit. The following tables/listing will be provided:

- The number of available samples as documented in the eCRF (item "Has urine sample been taken" is set . to "yes") will be tabulated separately by parameter and by visit (frequency statistics).
- The value for pH and specific gravity (in g/ml) will be tabulated by visit (summary statistics).
- The results (outcome: negative/1+/2+/3+/4+/not available for nitrite, protein, glucose, ketones, • urobilinogen, bilirubin and erythrocytes (white blood cells) will be tabulated by visit (frequency statistics).
- A data listing of urinalysis details (including sampling date, age, clinical relevance (yes/no) as well as the • specification if relevant) will be prepared.

8.6 Vital Signs

Vital signs are investigated at Screening, Visit 0 (Day 0), Visit 1 (Day 0), Visit 2 (Day 28), Visit 3 (Day 56), Visit 4 (Day 168), Visit 5 (Day 196), Visit 6 (Day 224) and ET visit. The following tables / listing will be provided:

- Blood pressures (systolic/diastolic, in mmHg) and pulse rate (in beats/min) will be tabulated by visit (summary statistics).
- A data listing with vital signs at screening (subject number, time of assessment, blood pressure and pulse . rate) will be provided.

8.7 Symptom-directed physical examination

Symptom-directed physical exam is investigated at Visit 0, Visit 1 (Day 0), Visit 2 (Day 28), Visit 3 (Day 56), Visit 4 (Day 168), Visit 5 (Day 196), Visit 6 (Day 224) and ET visit. The following tables / listing will be provided:

- The presence (yes / no / not assessed) of symptom-directed physical exams of ten symptoms will be • tabulated by symptom (headache, fever, myalgia, limb discomfort, joint pain (arthralgia), flu-like symptoms, nausea, vomiting, rash, excessive fatigue, other).
- A data listing of symptom-directed physical exams details will be prepared. .

8.8 Local tolerability

The investigator's assessments of local tolerability of previous injection site: injection side pain (pain without touching), tenderness (pain upon touching), itching (pruritus), redness (erythema), hardening (induration) and swelling (edema) will be analyzed at Visit 0, Visit 1 (Day 0), Visit 2 (Day 28), Visit 3 (Day 56), Visit 4 (Day 168), Visit 5 (Day 196), Visit 6 (Day 224) and ET visit by time-points (before vaccination (previous injection site) / 1 hour after vaccination). The following tables / listing will be provided:

- The results (yes/no/not assessed) will be tabulated by local tolerability symptom, visit and time-point • (frequency statistics).
- A data listing of local tolerability of previous injection site symptoms will be prepared.

8.9 System-based physical assessment

System-based assessment is investigated at Visit 0, Visit 1 (Day 0), Visit 2 (Day 28), Visit 3 (Day 56), Visit 4 (Day 168), Visit 5 (Day 196), Visit 6 (Day 224) and ET visit. The following tables / listing will be provided:

- The results (normal / abnormal / not done) of system-based assessments will be tabulated by body • system (general appearance and skin; head/eyes/ears/nose/throat; cardiovascular system; respiratory system; abdominal and gastrointestinal system; musculoskeletal system; neurological system; lymph nodes; other).
- A data listing of system-based assessments (including date of examination, clinical relevance and . description of abnormal findings) will be prepared.

8.10 Pregnancy Test

Urine pregnancy test are performed at Screening, Visit 0, Visit 1 (Day 0), Visit 2 (Day 28), Visit 3 (Day 56), Visit 4 (Day 168), Visit 5 (Day 196), Visit 6 (Day 224) and ET visit. The following tables / listing will be provided:

- The result of the pregnancy test (outcome: negative, positive, not applicable) will be tabulated by visit for female subjects (frequency statistics).
- A data listing of pregnancy test details (date of pregnancy test, result, test performed) will be prepared.

9. CONVERSION FACTORS FOR LABORATORY PARAMETERS

Conversion of laboratory parameters from a study site specific laboratory unit into the standard unit is performed via the following formula:

• Value in standard unit = value in study site specific unit * conversion factor

The following values will be used for conversion factors.

Parameter	Standard Unit	Site Unit	Conversion Factor
Alanine Aminotransferase	U/L	mU/mL	1
Alkaline Phosphatase	U/L	mU/mL	1
Aspartate Aminotransferase	U/L	mU/mL	1
Bilirubin	µmol/L	mg/dL	17.1
Creatinine	µmol/L	mg/dL	88.4025
Erythrocytes	T/L	Tera/L	1
Fibrinogen	g/L	mg/dL	0.01
Hematocrit	%	L/L	100
Hemoglobin	g/L	g/dL	10
Leukocytes	G/L	Giga/L	1
Platelets	G/L	Giga/L	1
Potassium	mmol/L	mval/L	1
Sodium	mmol/L	mval/L	1
Specific Gravity (Urine)	g/L	g/ml	1000

10. LIST OF TABLES, DATA LISTINGS AND FIGURES

10.1 List of Tables

No	IA	FA	Legend	Content
			Overall Study Information	
1.1	Х	Х	Number of subjects in each analysis population by study site and	
			overall	
1.2	Х	х	Number of subjects in each analysis population by treatment group	
			and overall	
1.3	х	х	Number of screening failures	
1.4		х	Number of subjects by visit (incl. early terminations) by treatment	
			group and overall (Safety population)	
1.5	х	х	Number of subjects by visit (incl. early terminations) by treatment	
			group and overall (mITT population)	
1.6		х	Number of subjects by visit (incl. early terminations) by treatment	
			group and overall (PP population)	
1.7		х	Early terminations and reasons by treatment group and overall	
			(Safety population)	
1.8	х	х	Early terminations and reasons by treatment group and overall	
			(mITT population)	
1.9		х	Early terminations and reasons by treatment group and overall (PP	
			population)	
1.10		х	Number of major protocol deviations by treatment group and	
4.4.4			overall (Safety population)	
1.11		х	Number of major protocol deviations by treatment group and	
			overall (mill population)	
0.1.1			Baseline Data	
2.1.1	X	X	Demography and baseline characteristics (mill Population)	Age, gender, ethnic group
2.1.2	x	х	Physical examination results at screening by body system	
010	~	~	Vite signs (mITT Deputation)	Custalia (diastalia bland
2.1.3	X	х	vital signs (mit i Population)	Systolic/diastolic blood
				tomporature
214	v	v	Modical history and concomitant modication by treatment group	
2.1.4	~	~	and overall (mITT Deputation)	appropriate the modioation
215	v	v	Modical history by SOC and PT (mITT Population)	
2.1.5	^ V	×	Concomitant modication by ATC lovel 2 (mITT Population)	
2.1.0	^	×	Poneet tables for the Safety penulation	
2.2.1-		^		
2.2.0		v	Repeat tables for the PP population	
2.3.1		^		
2.5.0			Immunogenicity Analysis	
Driman	L End	oint		
311		y v	Number of subjects with functional antibody blood samples drawn	
0.1.1	^	^	at Day 56 treatment group and overall (mITT population)	
312	x	x	Primary Endpoint: GMT of functional antibodies by PRNT at Day 56	
0.1.2	^	^	by treatment group and overall (mITT population)	
3.1.3	x	x	Primary Endpoint: ANOVA with fixed factor treatment group for GMT	
	Î.	~	of functional antibodies by PRNT at Day 56 (mITT population)	
1	1	1		

SAP (MV-CHIK-202, FINAL 3.0, 09-May-2018)

Based on:

STAT03_A Statistical Analysis Plan

Version 5.0, Effective Date 16-Dec-2016

Confidential and intellectual property of Assign DMB. No part of this document or its contents may be duplicated, referenced, published or otherwise disclosed in any form or by any means without prior written consent of Assign DMB.

Functional Antibodies					
211		v	Number of subjects with functional antibody blood samples drawn		
5.1.4	^	^	by visit, treatment group and overall (mITT population)		
3.1.5	х	x	GMT of functional antibodies by PRNT by visit, treatment group and		
0.110	~	^	overall (mITT population)		
3.1.6	Х	Х	ANOVA with fixed factor treatment group for GMT of functional		
			antibodies by PRNT by visit (mITT population)		
3.1.7		Х	ANOVA with fixed factors treatment group for GMT of functional		
			antibodies by PRNT between group A and B - 28 days after second		
			vaccination (mITT population)		
3.1.8		Х	ANOVA with fixed factors treatment group for GMT of functional		
			antibodies by PRNT between group C and D - 28 days after second		
			vaccination (mITT population)		
3.1.9		Х	ANOVA with fixed factors treatment group for GMT of functional		
			antibodies by PRNT between group M1 and M2 - 28 days after		
			second vaccination (mITT population)		
3.1.10	х		GMT of functional antibodies by PRNT - 28 days after first		
			vaccination by baseline measles titer group and overall (mITT		
			population)		
3.1.11	х		ANOVA with fixed factor baseline measles titer group for GMT of		
			functional antibodies by PRNT - 28 days after first vaccination		
			(mITT population)		
3.1.12		х	GMT of functional antibodies by PRNT - 28 days after second		
			vaccination by baseline measles titer group and overall (mITT		
			population)		
3.1.13		х	ANOVA with fixed factor baseline measles titer group for GMT of		
			functional antibodies by PRNT - 28 days after second vaccination		
			(mITT population)		
3.1.14	х	х	Seroconversion rate PRNT_SC by visit, treatment group and overall		
0.4.45			(mill population)		
3.1.15	х	х	GMT of functional antibodies by ELISA by visit, treatment group and		
2110	~	~	Overall (IIII I population)		
5.1.10	X	X	antibodies by FLISA by visit (mITT population)		
3117	x	x	Seroconversion rate FLISA_SC by visit treatment group and overall		
0.1.1	^	^	(mITT population)		
Measle	s Anti	bodie	es		
3.1.18	х	х	Number and proportion of subjects with measles antibody titer		
			samples drawn by visit, treatment group and overall (mITT		
			population)		
3.1.19	х	х	GMT for ELISA measles antibodies by visit, treatment group and		
			overall (mITT population)		
T-cell Ar	nalysi	S			
3.1.20	Х	Х	Number of subjects of functional Chikungunya virus specific T cells		
			by visit, treatment group and overall (mITT population)		
3.1.21	Х	Х	GMT for T cell immune by visit, treatment group and overall (mITT		
			population)		
3.1.22	х	Х	ANOVA with fixed factor treatment group for T-cells by visit (mITT		
			population)		
Measle	s Viru	s Sh	edding		
3.1.23		х	Number of subjects participating in measles virus shedding by		
			treatment group and overall (mITT population)		
3.1.24		х	Number of sample performed by visit, treatment group and overall		
			(mITT population)		

Based on: STAT03_A Statistical Analysis Plan

Version 5.0, Effective Date 16-Dec-2016

Confidential and intellectual property of Assign DMB. No part of this document or its contents may be duplicated, referenced, published or otherwise disclosed in any form or by any means without prior written consent of Assign DMB.

3.1.25		Х	Number of subjects with positive shedding results in urine by visit,	
			treatment group and overall (mITT population)	
3.1.26		Х	Number of subjects with positive shedding results in saliva by visit,	
			treatment group and overall (mITT population)	
3.2.1 -		х	Repeat the tables for the PP population	
3.2.26				
			Safety Analysis	
4.1		Х	Extent of Exposure (Safety population)	Study duration,
				Treatment duration
4.2	Х	х	Solicited Adverse Events ('Analysis' population)	AE, serious AE, severe AE, AE by severity
4.3	x	x	Unsolicited Adverse Events ('Analysis' population)	TEAE, serious TEAE, severe TEAE, TEAE related to study drug, medically attended TEAE, TEAE where an action was taken, TEAE of special interest (arthritis)
4.4	х	х	At least one unsolicited TEAE by SOC, PT, treatment group ('Analysis' population)	
4.5	х	х	At least one severe unsolicited TEAE by SOC, PT, treatment group ('Analysis' population)	
4.6	Х	х	At least one serious unsolicited TEAE by SOC, PT, treatment group ('Analysis' population)	
4.7	Х	х	At least one unsolicited TEAE related to study drug by SOC, PT, treatment group ('Analysis' population)	
4.8	х	х	At least one medically attended unsolicited TEAE by SOC, PT, treatment group ('Analysis' population)	
4.9	х	х	At least one unsolicited TEAE where an action was taken SOC, PT, treatment group ('Analysis' population)	
4.10	х	х	At least one unsolicited TEAE of special interest by SOC, PT, treatment group ('Analysis' population)	
4.11	х	х	At least one unsolicited TEAE related to study drug by SOC, PT,	
42-	v		Use in tables $A > A = A = A = A = A$	
4.2 4.11	^		nonulation	
4.11		x	Use in tables $4.2 - 4.11$ the Safety population as 'Analysis'	
4.11		^	nonulation	
4 1 2		x	Number of subjects with laboratory samples drawn by category	
		^	visit, treatment group (Safety population)	
4.13		х	Hematology laboratory: absolute values by parameter, visit,	
			treatment group (Safety population)	
4.14		Х	Clinical chemistry laboratory: absolute values by parameter, visit,	
			treatment group (Safety population)	
4.15		х	Coagulation laboratory: absolute values by parameter, visit,	
4 16		x	Hematology laboratory: absolute changes from screening by	
		^	parameter, visit, treatment group (Safety population)	
4.17		x	Clinical chemistry laboratory: absolute changes from screening by	
		 	parameter, visit, treatment group (Safety population)	
4.18		х	Coagulation laboratory: absolute changes from screening by	
			parameter, visit, treatment group (Safety population)	
4.19		х	Number of subjects with urine samples drawn by category, visit,	
			treatment group (Safety population)	
4.20		х	Quantitative urinalysis by parameter, visit, treatment group (Safety	

Based on: STAT03_A Statistical Analysis Plan

Version 5.0, Effective Date 16-Dec-2016

Confidential and intellectual property of Assign DMB. No part of this document or its contents may be duplicated, referenced, published or otherwise disclosed in any form or by any means without prior written consent of Assign DMB.

Page 41 of 47

		population)	
4.21	Х	Qualitative urinalysis by parameter, visit, treatment group (Safety	
		population)	

4.22		х	Systolic blood pressure by visit, treatment group (Safety	
			population)	
4.23		х	Diastolic blood pressure by visit, treatment group (Safety	
			population)	
4.24		Х	Pulse rate by visit, treatment group (Safety population)	
4.25		Х	Body temperature by visit, treatment group (Safety population)	
4.26		х	Presence of symptom-directed physical examination by symptom,	
4.07			visit, treatment group (Safety population)	
4.27		х	Local tolerability by symptom, visit and time-point, treatment group	
4.00			(Safety population)	
4.28		X	Presence of any local tolerability symptom by time-point, treatment	
4.00		~	group (Subject Diary, Salety population)	
4.29		X	everall by treatment group (Subject Diany, Safety period and	
1 20		v	Dressence of each local telerability symptom by time point	
4.30		×	treatment group (Subject Dian, Safety population)	
1 21		v	Presence of each local telerability symptom by diary period and	
4.51		×	overall by treatment group (Subject Diany Safety population)	
4 32		v	Severity of any local tolerability symptom by time-point, treatment	
4.52		^	group (Subject Diany, Safety population)	
4 33		x	Severity of any local tolerability symptom by diary period and	
4.55		^	overall by treatment group (Subject Diary, Safety population)	
4.34		x	Severity of each local tolerability symptom by time-point treatment	
		Â	group (Subject Diary, Safety population)	
4.35		х	Severity of each local tolerability symptom by diary period and	l
			overall by treatment group (Subject Diary, Safety population)	
4.36		х	Size of affected areas for redness (erythema), swelling (edema)	
			and hardening (induration), by time-point, treatment group (Subject	
			Diary, Safety population)	
4.37		Х	Presence of any systemic tolerability symptom by time-point,	
			treatment group (Subject Diary, Safety population)	
4.38		Х	Presence of any systemic tolerability symptom by diary period and	
			overall by treatment group (Subject Diary, Safety population)	
4.39		х	Presence of each systemic tolerability symptom by time-point,	
			treatment group (Subject Diary, Safety population)	
4.40		х	Presence of each systemic tolerability symptom by diary period and	
			overall by treatment group (Subject Diary, Safety population)	
4.41		х	Severity of any systemic tolerability symptom by time-point,	
1.40			treatment group (Subject Diary, Safety population)	
4.42		X	Severity of any systemic tolerability symptom by diary period and	
1 1 2		~	Overall by treatment group (Subject Diary, Salety population)	
4.43		X	sevency of each systemic coerability symptom by time-point,	
1 1 1		v	Coverity of each systemic tolorghility symptom by diary paried and	
4.44		X	sevency of each systemic coerability symptom by diary period and	
4.45		x	Body temperature by time-point treatment group (Safety	
+5		^	nonulation)	
4 4 6		x	System-based assessment results by body system visit treatment	 
1.70			group (Safety population)	
4.47		x	Result of pregnancy test by visit, treatment group (Safety	
			population)	
1	1	1		•

Based on: STAT03_A Statistical Analysis Plan

Version 5.0, Effective Date 16-Dec-2016

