#### 4.1.2 Secondary endpoints

- Immunogenicity on day 0, 28, 196 and 224; additionally, for group M1 and M2 on day -28 and 168 as confirmed by the presence of functional anti-chikungunya antibodies as determined by the plaque reduction neutralization test (PRNT50) and by ELISA.
- Measurement of anti-measles antibodies on day 0, 28, and 56; additionally, for group M1 and M2 on day -28 as determined by ELISA.
- Solicited local and systemic adverse events (AEs)
- Serious adverse events (SAEs)
- Rate of AEs during the 28 day post-vaccination period
- Safety laboratory parameters (hematology, serum chemistry, urinalysis)
- Shedding of live recombinant virus until day 196 (subset of subjects)
- Induction of a Chikungunya virus specific T cell responses (subset of subjects)
- Pre-existing anti-vector immunity:
  - Immunogenicity of Chikungunya vaccine in the presence of recently boosted measles immunity (measles booster groups M1 and M2).
  - Relation of post-vaccination anti-chikungunya plaque reduction neutralization titers (PRNT50) and baseline anti-measles ELISA titers (all treatment groups).

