### 13.1 Immunogenicity Analysis

The primary immunogenicity analysis will compare the anti-chikungunya PRNT50 antibody geometric mean titer (GMT) 28 days after one or two immunizations in the Per Protocol (PP) analysis population between the treatment groups. GMTs and GMT ratios will be estimated by applying an analysis of variance including the factor vaccination group. This will be done using log-10 transformed data and taking the anti-log of the resulting point estimates for the least squares means, least squares means differences and the corresponding 2-sided 95% CIs. P-values will also be provided to compare GMTs for the MV-CHIK groups (pairwise comparisons adjusted for multiple comparisons according to Tukey-Kramer; groups A vs. B, C vs. D, M1 vs. M2), e.g. 28 days after the 2nd MV-CHIK dose, etc. Likewise, SCRs will also be compared between groups. Seroconversion will be defined as anti-Chikungunya PRNT50 titers  $\geq 10$ .

Measles ELISA titers will be analyzed as described above. In addition, the effect of pre-existing anti-measles immunity will be assessed: The CHIKV PRNT50 titers 28 days after first vaccination, between the four baseline measles titer groups, defined by baseline percentiles

(25%, 25-50%, 50-75%, 75-100%), will be compared. No stratification by dose groups is intended.

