2.2 Conduct of Analysis

2.2.1 Preliminary Analysis

A preliminary analysis including safety and immunogenicity data will be performed in August 2017. The analysis was initially planned to be conducted after all subjects completed Visit 3 (Day 56) but was re-scheduled due to unforeseen delays to enable further vaccine development progress. The goal of this analysis is to provide highly valuable data of the novel Chikungunya vaccine for further development. Results from this analysis will have no impact on the study design and treatment of the subjects in this study.

All tables and listings marked with an "x" in column "IA" in section 10.1 and 10.1 will be generated for this Preliminary Analysis.

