2.7.2 Inferential Analysis for the Secondary Immunogenicity Endpoints

- An ANOVA with the fixed factors treatment group (CV1, CV2, A, B, C, D, M1, M2) will be used to compare ٠ PRNT functional antibody geometric mean titers (GMT) per visit (incl. Day -28).
- An ANOVA with the fixed factors treatment group (CV1, CV2, A, B, C, D, M1, M2) will be used to compare . ELISA functional antibody geometric mean titers (GMT) per visit (incl. Day -28).
- Seroconversion rates (SCR) will be compared between treatment groups. Seroconversion will be defined as anti-Chikungunya PRNT₅₀ titers \geq 10.
- The CHIKV PRNT50 GMT 28 days after first vaccination (i.e. Day 28 for group A and C; Day 56 for group B and D), between the four baseline (Day 0) measles titer groups, defined by baseline percentiles (0 to <25%, 25 to < 50%, 50 to <75%, 75 to 100%), will be compared by an ANOVA with fixed factors baseline measles titer group. No stratification by dose groups is intended.
- An ANOVA with the fixed factors treatment group (CV1, CV2, A, B, C, D, M1, M2) will be used to compare T-• cells (geometric mean values) per visit.

And additionally for Final Analysis:

The CHIKV PRNT₅₀ GMT 28 days after second vaccination (i.e. Day 56 for group A and C; Day 224 for group B and D), between the four baseline (Day 0) measles titer groups, defined by baseline percentiles (0 to <25%, 25 to < 50%, 50 to <75%, 75 to 100%), will be compared by an ANOVA with fixed factor baseline measles titer group. No stratification by dose groups is intended.

- An ANOVA with the fixed factors treatment group will be used to compare PRNT antibody geometric mean titers (GMT) 4 weeks after second vaccination between group A and B (i.e. comparing the GMT for A at Day 56 with the GMT of group B at Day 224).
- An ANOVA with the fixed factors treatment group will be used to compare PRNT antibody geometric mean titers (GMT) 4 weeks after second vaccination between group C and D (i.e. comparing the GMT for C at Day 56 with the GMT of group D at Day 224).
- An ANOVA with the fixed factors treatment group will be used to compare PRNT antibody geometric mean titers (GMT) 4 weeks after second MV-CHIK vaccination between group M1 and M2 (i.e. comparing the GMT for M1 at Day 56 with the GMT of group M2 at Day 224).

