The statistical analysis plan is based on the final study protocols for Austria (Version 1.5; 24-Nov-2016) and Germany (Version 1.6; 19-Apr-2017). No changes in the conduct of the planned analysis as described in the CSP are intended.

However, the time point of the Preliminary Analysis was moved forward to August 2017. The Preliminary Analysis was initially planned to take place after all subjects completed Visit 3.

Page 21 of 47

3. **OVERALL STUDY INFORMATION**

Treatment groups for the preliminary analysis as well the final analysis are defined in section 2.3. Overall study information analysis will be prepared for the:

- Preliminary analysis: mITT population. •
- Final analysis: Safety, mITT and PP population. •

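### SAP text and table list disagree: the first-dose analysis by baseline measles titre belongs to the final mITT analysis in SAP 2.7.2 but is listed for the preliminary analysis only

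*SAP*

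**What the plan says.** Protocol 4.1.2 lists pre-existing anti-vector immunity among the secondary endpoints. One part of it is "Relation of post-vaccination anti-chikungunya plaque reduction neutralization titers" to baseline measles ELISA titres. Protocol 13.1 names the analysis: it compares chikungunya PRNT50 "titers 28 days after first vaccination, between the four baseline measles titer groups, defined by baseline percentiles". Nothing there confines it to an interim look.

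SAP 2.7.2 carries this comparison in its general list of secondary immunogenicity analyses and fixes the sampling day: Day 28 for groups A and C, Day 56 for B and D. The second-dose version comes later, under the line "And additionally for Final Analysis".

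SAP 10.1 lists the mITT tables. Table 3.1.10, "GMT of functional antibodies by PRNT - 28 days after first" vaccination, and its ANOVA, Table 3.1.11, whose title begins "ANOVA with fixed factor baseline measles titer group for GMT of", are marked under IA and blank under FA. Tables 3.1.12 and 3.1.13, for "functional antibodies by PRNT - 28 days after second vaccination", are marked under FA and blank under IA.

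SAP 2.2.1 reports that the preliminary analysis, first planned for when all subjects had completed Visit 3, "was re-scheduled due to unforeseen delays to enable further vaccine development progress" and set for August 2017. SAP 2.17 says it was moved forward. The same section states: "No changes in the conduct of the planned analysis as described in the CSP are intended".

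**The concern.** The table list gives a different instruction from the SAP text. A programmer working from SAP 10.1 would produce the first-dose comparison in mITT once, on the August 2017 data, and only the second-dose comparison in mITT at the end. A reader of SAP 2.7.2 would expect both at the end. SAP 2.17, which should disclose any intended reduction, reports only the changed date of the preliminary analysis.

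At stake is one population's version of a protocol-specified secondary analysis. The study report could hold a first-dose mITT result based on fewer subjects than the trial finally provides, next to a second-dose mITT result on complete data. The two would then differ in the subjects included as well as in the dose.

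**Working it through.** The plan attaches no figure to this analysis, so the check sets the passages side by side. The arithmetic serves only to size the exposure.

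**1. The marks in SAP 10.1.**

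| Tables (mITT) | Content | IA | FA |
|---|---|---|---|
| 3.1.10, 3.1.11 | 28 days after first vaccination, by baseline measles titre group | x | blank |
| 3.1.12, 3.1.13 | 28 days after second vaccination, by baseline measles titre group | blank | x |

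The two pairs mirror each other and neighbouring rows (3.1.5, 3.1.6, 3.1.14) carry both marks, so a fault in reading the PDF is unlikely. No other table in the 3.1 series is marked for the preliminary analysis alone.

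**2. What the marks control.** SAP 2.2.2 generates for the final analysis the tables marked under FA. Read literally, 3.1.10 and 3.1.11 are not final-analysis output.

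**3. What the text says.** In SAP 2.7.2 the first-dose comparison stands above the final-analysis line, and that line adds to the list without replacing anything in it. SAP 6.2.2 sends the final analysis back to 2.7.2 with no exception. SAP 6 presents final immunogenicity in both mITT and PP. Together these imply a final first-dose analysis in mITT, which the table list does not schedule.

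**4. Why the preliminary run may be short of data.** Groups B and D receive placebo on Day 0 and their first vaccine on Day 28, so their sample 28 days later is Day 56, which is Visit 3. Visit 3 completion by all subjects is the condition that was dropped.

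**5. Size of the exposure.** SAP 2.7 defines the baseline percentiles on groups A, B, C and D, and SAP 2.3 places control recipients in separate groups (CV1, CV2). Protocol Table 1 plans 60 MV-CHIK subjects in each of A to D:

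- Total: 4 × 60 = 240. In B and D: 2 × 60 = 120, or 120/240 = 50%.
- Each 10% of B and D without a Day 56 titre: 0.10 × 120 = 12 subjects, or 12/240 = 5%.

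**6. Effect on precision, as an illustration.** Assume equal quartiles, a log10 SD of 0.6 (the value used in Protocol 13.4), and an unadjusted two-sided 5% comparison of two quartiles with n subjects each. The GMT ratio detectable with 80% power, by normal approximation, is 10^[0.6 × √(2/n) × (1.960 + 0.842)].

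| Share of the 240 available | n per quartile | Detectable GMT ratio |
|---|---|---|
| 100% | 60 | 2.03 |
| 80% | 48 | 2.20 |
| 60% | 36 | 2.49 |
| 50% | 30 | 2.72 |

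The documents do not say where in this range August 2017 falls.

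**7. The PP repeat.** SAP 10.1 marks Tables 3.2.1 to 3.2.26 under FA as the PP repeat. The mITT series runs from 3.1.1 to 3.1.26, so the numbers match one to one and the range includes 3.2.10 and 3.2.11. SAP 2.16 uses the PP population in the final analysis only, so those two tables could only be final-analysis output.

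**The case against.** The strongest reply is that little is lost. The SAP text already provides for the final mITT analysis, so this may be no more than two missing marks. The PP repeat appears to supply a complete-data version in the population that Protocol 13.5.3 makes primary for immunogenicity, while Protocol 13.5.2 calls the mITT analyses exploratory. The size of any shortfall in August 2017 is unknown and could be trivial. All of this stands, and it limits the point to a consistency defect affecting one population. It does not remove the defect: SAP 6 promises mITT as well as PP at the final analysis, and the table list does not deliver the mITT part.

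Three stronger readings are tempting but lack support:

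- **That the first-dose comparison is never made on complete data.** The numbering of the PP repeat points the other way. What remains open is whether the repeat line was meant to cover tables that are not themselves marked FA.
- **That the first-dose result matters most because measles antibody interferes chiefly at the first dose.** No passage says so. The Phase 1 summary in Protocol 2.4 reports no interference on day 28 after the first immunization.
- **That mITT carries special weight here because SAP 6.1 names it.** That section concerns the Day 56 primary endpoint, and its choice of mITT itself departs from Protocol 13.5.3. It does not set the population for this secondary analysis.

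**Conclusion.** The point holds as an inconsistency between the SAP text and its table list, of low to moderate severity. SAP 2.7.2, 6 and 6.2.2 imply a final first-dose analysis by baseline measles titre in mITT; SAP 10.1, read with 2.2.2, schedules that mITT analysis for August 2017 only. SAP 2.17 does not disclose a reduction, and this SAP version is dated 09-May-2018, so the blank cells stand in a text later than the scheduled preliminary analysis.

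The conclusion rests on two inferences. First, that some subjects lacked the needed sample in August 2017: this follows from the analysis being moved ahead of the Visit 3 condition, but no count is given. Second, that the PP repeat includes 3.2.10 and 3.2.11: this follows from the numbering and is not stated. A reader might infer that the sponsor chose to put the second-dose result in place of the first-dose one. The wording of SAP 2.7.2 and the statement in SAP 2.17 make an oversight in the table list at least as likely.

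**What to change.** In SAP 10.1, mark Tables 3.1.10 and 3.1.11 with an x under FA as well as IA, and confirm in the PP repeat line that 3.2.10 and 3.2.11 are produced. If the final mITT version is in fact meant to be dropped, say so in SAP 2.17, give the reason, and bring 2.7.2 and 6.2.2 into line.

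The cost is two marks and one clarifying phrase. The tables are already specified for the preliminary analysis, so the final run should need the same programs on the complete data and no new sampling or assays.
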